A formal cost-effectiveness analysis will be relevant if the clinical trial reveals a significant benefit of PCDT in terms of the primary study endpoint and if that benefit comes at additional cost. This analysis will use the societal perspective as recommended by the National Panel on

Cost-Effectiveness in Health and Medicine (167) and will be based, to the extent possible, on the empirical data from the trial. Cost effectiveness will be calculated as:

Lifetime Cost (PCDT) – Lifetime Cost (optimal standard therapy) Effectiveness (PCDT) – Effectiveness (optimal standard therapy) where effectiveness is measured in terms of quality-adjusted life years (QALYs).

A. Derivation of In-trial Quality-adjusted Life Expectancy: The in-trial contribution to each patient's quality-adjusted life expectancy will be estimated by multiplying his/her within-trial survival time by the time-weighted average of associated utility weights obtained from the SF-36. For example, the utility value assigned for the first 6 months will be the mean of the baseline and 6 month utility score; the utility for months 6-12 will be the mean of the 6-month and 12-month utility assessments; and so on.

B. Projecting Beyond the Trial for QALYs and Costs: Although the randomized trial will follow patients for 2 years, outcomes pertinent to cost-effectiveness may continue to evolve well after its conclusion. In particular, it is anticipated that most patients will remain alive at the trial's conclusion and that the benefit of PCDT will accrue over the long term, through a reduction in morbidity and costs associated with PTS. Thus, a method is required for converting the observed trial experience into corresponding lifetime quality-adjusted survival and cost figures needed for the incremental cost-effectiveness calculations. Although the use of "within-trial" cost-effectiveness ratios would eliminate the need for extrapolation, this approach would bias our analysis substantially against PCDT given its high up-front cost and the expectation that any quality of life benefits are likely to be sustained. Moreover, lifetime ratios are necessary for comparison with external benchmarks.

To extend the trial results beyond the observed time-frame, we will develop a Markov (statetransition) model (189) in which the principal health states will describe the long-term complications of DVT as defined by the clinical trial (e.g., death, recurrent DVT, venous ulcer, cellulitis, pulmonary embolism). This model will be patterned after previous models developed by the EQOL investigators to project long-term complications, costs, and life-expectancy in patients with chronic coronary disease, acute myocardial infarction, and cerebrovascular disease (190-192). In addition to the ATTRACT Trial itself and published literature, a potential source of cost, transition probability and utility inputs for the model is long-term follow-up results from the Venous Thrombosis Outcomes (VETO) study, a 5 year (2002-2007), multicenter prospective follow-up study of 387 patients with acute symptomatic DVT that is collecting detailed resource use and costs data relating to PTS. We will have full access to the 5 year VETO data through the study's principal investigator, [name] (ATTRACT Steering Committee member). Although the primary cost data for

140

VETO are applicable to the Canadian health care system, they can be converted to approximate U.S. equivalents using Purchasing Power Parities (193). These data will be essential to projecting the incremental costs associated with PTS (stratified by severity level) that are critical to model the long-term QOL impact of PCDT in preventing late DVT complications.

C. Incremental Cost-Effectiveness Analysis: Once the estimates of long-term costs and QALYs have been obtained for each of treatment arm, an incremental cost-effectiveness analysis will be carried out. For this analysis, costs and survival beyond the first year will be discounted at 3% per year according to current standards. Bootstrap analysis will be used to assess the precision of the cost-effectiveness ratios, and the results of the analysis will be presented graphically in the cost-effectiveness plane, including percentages of the distribution falling in the dominant (clinical benefit at lower costs) and dominated (higher costs but no clinical benefit) quadrants. In addition, results from the bootstrap analysis will be presented in the form of cost- effectiveness across a range of cost-effectiveness thresholds (194-197).

D. Secondary Cost-Effectiveness Analyses: In addition to the pre-specified primary costeffectiveness analyses, we will perform a variety of exploratory secondary analyses. This will include subgroup analyses to identify cost-effective strategies for specific types of patients and will be based on the pre-specified patient subgroups identified in the clinical protocol.

E. Sensitivity Analyses: Extensive and comprehensive sensitivity analyses, including probabilistic sensitivity analysis on parameters such as Markov model transition rates, will be performed on all key factors in the cost-effectiveness analysis. For factors that are measured empirically during the study, such as QOL and costs, analyses will consider not only mean values but also values that are one standard-deviation removed from the mean and the 95% confidence intervals for the parameters. Less marked variations will also be considered, and one-way and two-way thresholds for indifference between the various strategies will be determined. We will also consider alternative discount rates ranging from 0-7%.

February 14, 2013

141

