4.5 Baseline Evaluation

After eligibility is established and informed consent is obtained, but before randomization, subjects should undergo the following baseline assessments (see Section 8 for details):

- Self-completion of QOL questionnaires (SF-36v2, VEINES);
- Self-rating of baseline leg pain (7-point Likert scale) (both legs);
- Calf circumference measurement (both legs);
- Administration of Villalta's PTS Scale (both legs); and
- Venous Duplex ultrasound of the index leg. A previous ultrasound may be used if it was
 performed within 5 days prior to randomization, provided that its scope was adequate
 (i.e. compression of the proximal veins of the leg was clearly documented, enabling entry
 of this information on the Compression Ultrasound Case Report Form).
- Examination of the contralateral lower extremity is encouraged but optional; if performed, the findings should also be entered on the Compression Ultrasound Case Report Form.

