15.3.5 Generic Quality of Life

The change in SF-36v2 PCS and MCS scores from baseline to 24 months will be compared between the two groups using a Student's t-test. A difference of 5 points on each scale is considered to be clinically relevant. In addition, a linear mixed model analysis of the repeated assessments (at 1, 6, 12, 18 and 24 months) with baseline scores as a covariate will be used to investigate the changes over time, and if they differ by treatment arm.

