15.4 Additional Analysis Issues

15.4.1 Confounding

Stratification at randomization for the extent of DVT and Clinical Center and the standardization of the use of standard DVT therapy (Section 12.5) will reduce the potential for confounding. However, in addition to the unadjusted analysis described above, an adjusted analysis of the study outcomes comparing treatment Arms will be performed using multivariable regression analysis (linear regression for continuous outcomes, logistic regression for binary outcomes) that controls for the following baseline variables as main effects: age (continuous), gender (female vs. male), ethnicity (Hispanic/Latino vs. other), race (American Indian/Alaskan Native, Asian, Black, Hawaiian/Pacific Islander vs. White), body-mass index, employment status, previous ipsilateral DVT, inpatient (yes, no), duration of leg symptoms, extent of DVT at presentation (iliofemoral vs. femoropopliteal), symptom severity at presentation, and Clinical Center.

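### The in-trial QALY contrast in Appendix 13 is written as a plain arm difference with no adjustment for baseline SF-36 utility, which gives away precision at no saving

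*Protocol*

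**What the plan says.** Appendix 13, under its own heading for analytic plan and statistical methods, sets out the cost-effectiveness analysis in lettered parts.

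- Part A obtains the in-trial QALY by "multiplying his/her within-trial survival time by the time-weighted average of associated utility weights obtained from the SF-36". Its example states that "the utility value assigned for the first 6 months will be the mean of the baseline and 6 month utility score", and the later six-month intervals follow the same averaging rule.
- The effectiveness term of the ratio is "Effectiveness (PCDT) – Effectiveness (optimal standard therapy", measured in QALYs. No covariate is attached to it.
- Part B rejects within-trial ratios and extends costs and QALYs to a lifetime with a Markov model.
- Part C begins "Once the estimates of long-term costs and QALYs have been obtained for each of treatment arm", then specifies 3% discounting and a bootstrap for precision. Parts D and E add subgroup and sensitivity analyses. None of these parts mentions baseline utility as a covariate.

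The baseline value exists for every subject by design: section 4.5 lists "Self-completion of QOL questionnaires (SF-36v2, VEINES" among the assessments before randomization. For the clinical SF-36 analysis, section 15.3.5 specifies "a linear mixed model analysis of the repeated assessments (at 1, 6, 12, 18 and 24 months) with baseline scores as a covariate". Section 15.4.1 promises that "an adjusted analysis of the study outcomes comparing treatment Arms will be performed using multivariable regression analysis". Its covariate list ends with "symptom severity at presentation, and Clinical Center" and contains neither a baseline SF-36 score nor a utility.

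**The concern.** Baseline utility is measured before treatment can act, yet it enters the QALY directly and is likely to predict the later utilities. A chance difference between arms at baseline therefore reaches the unadjusted QALY contrast by two routes: the baseline term itself, and the correlated follow-up values. Regression on baseline utility removes the predictable part of that noise. The protocol already accepts this argument for the same instrument in section 15.3.5, but Appendix 13 does not carry it over to the QALY.

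At stake is the precision of the in-trial component of the cost-effectiveness result, and how far that component may sit from the true effect in the one sample observed. The primary endpoint, safety comparisons and sample size are unaffected.

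**Working it through.** **The plan's own figure.** Sample size sets how large a chance imbalance is likely to be. Section 15.1 gives 311 evaluable per arm for 30% versus 20% PTS, two-sided 0.05, 80% power, Fisher's exact test. Exact power at 311 per arm is 80.0%. Allowing for 10% loss, 311/0.9 = 345.6, so 346 per arm and 692 in total. Both figures reproduce.

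**Inputs from the protocol.** 346 per arm; utilities at 0, 6, 12, 18 and 24 months; the averaging rule in part A.

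**Assumptions not in the protocol.** Utility SD 0.10-0.18, equal at all visits; correlation r between baseline and each later visit 0.2-0.5; correlation 0.6 among later visits; complete 2-year data.

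**Step 1, weights.** Averaging the two ends of each half-year gives 0.25, 0.5, 0.5, 0.5 and 0.25 years, total 2.0. Baseline carries 0.25/2.0 = 12.5%.

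**Step 2, slope of QALY on baseline utility.** The later weights sum to 1.75, so slope = 0.25 + 1.75r.
- r = 0.2: 0.60
- r = 0.5: 1.125

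**Step 3, variance of the QALY in units of SD².**
- Baseline term: 0.25² = 0.0625
- Cross term: 2 × 0.25 × 1.75 × r = 0.875r
- Later visits: the squared weights sum to 0.8125, so 0.8125 + 0.6 × (1.75² − 0.8125) = 2.1625
- Total: 2.225 + 0.875r

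**Step 4, share of variance removed by adjustment.** R² = slope² / total variance.

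| r | slope | variance | R² |
|---|---|---|---|
| 0.2 | 0.60 | 2.400 | 0.15 |
| 0.3 | 0.775 | 2.4875 | 0.24 |
| 0.4 | 0.95 | 2.575 | 0.35 |
| 0.5 | 1.125 | 2.6625 | 0.475 |

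In equivalent sample size, 1/(1 − R²) − 1 is 18% at r = 0.2 and 91% at r = 0.5.

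**Step 5, size of a chance imbalance.** SE of the baseline difference = SD × √(2/346) = 0.0076 at SD 0.10 and 0.0137 at SD 0.18.
- Through the baseline term alone, one SE moves the QALY difference by 0.25 × 0.0076 = 0.002 to 0.25 × 0.0137 = 0.003.
- Through both routes, one SE moves it by 0.60 × 0.0076 = 0.005 to 1.125 × 0.0137 = 0.015.

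**Step 6, standard error of the in-trial QALY difference, SD 0.15, 346 per arm.**
- r = 0.3: 0.0180 unadjusted, 0.0157 adjusted
- r = 0.5: 0.0186 unadjusted, 0.0135 adjusted

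**Step 7, wider assumptions.** With SD up to 0.20 and r up to 0.7 (later-visit correlation raised to 0.7 to match), a one-SE shift reaches 0.022. If r were zero, adjustment would remove only 3% of the variance. The gain therefore depends mainly on r.

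**The case against.** The strongest reply is that the protocol is silent and has not decided against adjustment. Part A only defines each patient's QALY, the difference of two effectiveness terms is how any incremental ratio is written, and adjusted arm estimates would fit that expression. Section 15.6 promises a separate statistical analysis plan, which is not at hand. This stands as far as intent goes: nothing in the text rejects adjustment. It does not dispose of the point, because Appendix 13 is itself presented as the analytic plan and already fixes the QALY rule, the contrast, the bootstrap, the imputation approach and the discount rate. Followed as written, it yields the unadjusted contrast.

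The adjusted analysis in section 15.4.1 might be thought to cover the gap. It helps only in part: DVT extent and presenting symptom severity are on its list, but baseline utility is not.

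Three stronger readings are tempting, and the documents do not support them.

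- **A reader might infer bias.** Allocation is randomized and stratified by DVT extent and center, so the unadjusted difference is unbiased, and intervals from the planned bootstrap include the baseline variation.
- **A reader might take the in-trial difference as the denominator of the ratio.** Part B calls for lifetime ratios with Markov extrapolation, so the in-trial QALY is only one component. The analysis is also run only if PCDT is effective on the primary endpoint and costs more.
- **A reader might conclude that a chance imbalance could reverse the sign of the cost per QALY.** A 10-point PTS reduction at an assumed disutility of 0.05-0.10 over 1.5-2 years is worth 0.10 × 0.05 × 1.5 = 0.0075 to 0.10 × 0.10 × 2 = 0.020 QALY, close to the shifts above. But the disutility is not in the protocol, and the comparison covers two years only. Nothing has been calculated for the planned lifetime ratio.

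**Conclusion.** The point holds as a minor one about efficiency. Appendix 13 gives a pre-treatment utility 12.5% of the in-trial QALY weight and states a plain difference between arms, while the baseline covariate is already collected and is used for the same questionnaire in section 15.3.5. The consequence is a less precise in-trial component of the lifetime QALY difference, and error conditional on the imbalance actually observed.

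Under the narrower assumptions above, that error is about 0.005-0.015 QALY for a one-SE imbalance, and adjustment would remove about 15-48% of the variance. These sizes rest wholly on assumed SDs and correlations. What rests on the protocol alone is the 0.25-year weight and the absence of a stated baseline-utility adjustment.

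**What to change.** In Appendix 13, Cost-Effectiveness Analysis, parts A and C:

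1. State that the in-trial QALY difference is estimated by regression of the QALY on arm, baseline SF-36 utility and DVT-extent stratum.
2. Refit that regression within each bootstrap replicate, so that the intervals reflect the adjusted estimator.
3. Carry the adjusted difference into the in-trial part of the lifetime ratio and the associated bootstrap displays.
4. Report the unadjusted difference as a sensitivity result.

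The cost is a sentence or two of text. No new data, visits or subjects are needed, and the sample size does not change. Writing it down before unblinding also removes a later choice between raw and adjusted results.

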8.10 Health-Related Quality of Life (QOL)

We will assess general and venous disease-specific QOL at baseline and at the 1-month, 6-month, 12-month, 18-month and 24-month follow-up visits.

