10.2 Utility Measurement

Although QOL will be assessed using a variety of disease-specific and generic instruments in ATTRACT, for the purposes of economic analysis QOL will be assessed in terms of utility-- a

ATTRACT

[name]

measure of an individual's preference for his or her current health state relative to perfect health on a 0-1 scale (125). Although in the past, it had been customary to measure utility directly from the trial participants using time-tradeoff techniques, there is an emerging consensus that costeffectiveness analyses designed to inform societal resource allocation should use communitybased (rather than patient-based) preferences (126). For ATTRACT, we will calculate preference-based utility scores from the SF-36v2 data being collected as part of the QOL study, using a recently-validated U.S.-specific scoring algorithm developed by Brazier et al (127). This method has the advantage of using population-based utility weights that are appropriate to the perspective of our analysis (i.e. U.S. societal weights).

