11.2 Scheduled Visit 2 – Follow-Up Assessment at 1 Month

At 30 days \pm 7 days after randomization, subjects:

- rate their leg pain (7-point Likert scale) (both legs)
- have their leg circumference measured (both legs)
- undergo assessment using the Villalta PTS Scale (both legs)
- complete a QOL questionnaire (SF-36v2, VEINES-QOL/Sym)
- have a bilateral lower extremity Duplex ultrasound exam
- are queried on their use of ECS, and then ECS use is reinforced
- have adverse events, thrombotic and bleeding events, hospitalizations, physician visits, anticoagulant regimen, and their cost diary reviewed and recorded
- are re-assessed for removal of a retrievable IVC filter (if one is present)

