of resource-based costs and hospital billing data (177). Index Procedures - From the detailed resource use and procedure duration data recorded for the index procedure, costs will be calculated as the product of resource use and unit cost for each component. Acquisition costs for each item will be estimated as the average over several study hospitals.

B. Post-procedure Hospital Care: Costs for all other aspects of care during the initial hospitalization will be estimated based on hospital billing data. After excluding charges associated with the index procedure (for patients randomized to PCDT), post-procedure hospital costs will be determined by multiplying the remaining hospital charges by the hospital and cost-center specific cost-to-charge ratio obtained from the hospital's Medicare cost report (177). For patients for whom billing data are unavailable (expected to be < 10%), post-procedural hospital costs will be estimated based on a regression model developed from hospital admissions for which billing information is available, using multiple imputation. Multiple imputation techniques will be used rather than a single cost coefficient for each resource to preserve patient-to-patient variability within the study population. Costs will be converted to U.S. dollars corresponding to the last year of the trial, using the medical care component of the Consumer Price Index.

For any rehospitalizations for which standardized hospital billing information cannot be obtained (expected to be < 5% of total hospital admissions) or are non-existent (i.e., admissions to VA hospitals, non-U.S. hospitals, or other U.S. hospitals that do not generate UB-92 summary bills), inpatient medical care costs will be estimated based on a regression model derived from the hospitalizations for which bills are available, using multiple imputation, as will be done for the estimation of post- index procedure hospital costs, described above. Candidate resources for the imputation model would include length of stay, ICU length of stay, in-hospital events and complications, and major tests and procedures performed during the admission.

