C. Elimination of Hospitalization Costs Unrelated to Venous Disease: Hospital admissions unrelated to treatment of venous disease or its complications will be excluded from our economic analysis, since any differences in these events are unlikely to be related to the treatment strategy. Thus, their inclusion would only increase the variance of our cost estimates. A clinical events committee blinded to treatment assignment will review each hospital admission during the study to determine whether it should be excluded from the economic analysis.

D. Estimation of Other Costs: Costs for professional services (i.e. physician fees for inpatient care, procedures, outpatient visits, and testing) will be based on measured resource utilization (taken from the medical record and patient self-reports) and national average reimbursements (from Medicare Fee Schedule). Outpatient care costs will be assigned using the Medicare Fee

137

Schedule. Drug costs will be based on wholesale prices in the Drug Topics Red Book (178).

Costs of home health care, long-term care, and custodial care will be based on average Medicare reimbursements for the services provided. Costs of additional home health and custodial services not covered by Medicare will be based on average charges, estimated from sources such as the U.S. Nursing Home Survey (171). The cost of care provided by family members will be estimated as the cost of lost employment required to provide this care. These costs will be estimated based on average national wages among persons in the work force.

All costs will be valued in year 2010 dollars, which is anticipated to be the final year for which national average cost data are expected to be available at the completion of the study. Costs measured during years other than 2010 will be converted to constant dollars using the appropriate component of the Consumer Price Index. Costs will not be discounted for the primary cost comparisons, but will be discounted at a rate of 3% per year for the cost-effectiveness analyses (see below) as recommended by the U.S. Public Health Service Guidelines on Cost-Effectiveness in Medicine (167).

6. Utility Measurement

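### The in-trial QALY rule gives the 1-month SF-36v2 no weight, so utility differences that fade by 6 months are not counted; separately, Appendix 13 names two price years

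*Protocol*

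**What the plan says.** Section 10.2 of the Protocol takes utilities from the trial's own quality-of-life data: "we will calculate preference-based utility scores from the SF-36v2 data being collected as part of the QOL study". Section 8.10 sets the schedule: "We will assess general and venous disease-specific QOL at baseline and at the 1-month, 6-month, 12-month, 18-month and 24-month follow-up visits". Section 11.2 and Appendix 14 repeat the 1-month questionnaire, and the mixed model for generic quality of life in Section 15.3.5 uses it.

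Appendix 13 (Cost-Effectiveness Analysis, part A) defines each patient's in-trial QALY by "multiplying his/her within-trial survival time by the time-weighted average of associated utility weights obtained from the SF-36". A worked example follows: "the utility value assigned for the first 6 months will be the mean of the baseline and 6 month utility score", then "the utility for months 6-12 will be the mean of the 6-month and 12-month utility assessments", with later intervals treated in the same way. No part of Appendix 13 brings in the 1-month utility, and its sensitivity analyses (part E) do not address this interval.

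On prices, the same appendix says under Post-procedure Hospital Care (Estimation of Costs, part B): "Costs will be converted to U.S. dollars corresponding to the last year of the trial". Under Estimation of Other Costs (part D) it says: "All costs will be valued in year 2010 dollars", on the ground that 2010 should be the latest year with national cost data when the study completes. The Synopsis gives a start in November 2009 and a stop in May 2016.

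**The concern.** The baseline score is taken during acute DVT, before treatment. Joining it to month 6 by a straight line spreads recovery evenly over six months and ignores the one measurement made in between. That interval is where the arms are most likely to differ for a short time: PCDT follows within 3 days of randomization (Section 5.1), faster relief of presenting symptoms is expected (Section 18.1), and bleeding is examined over the first 10 days (Section 15.3.2). The omission can hide a short-lived gain or a short-lived loss, so its direction is not known in advance. The QALY difference is the denominator of the cost per QALY, a listed secondary outcome (Section 8.2).

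The price-year conflict touches the numerator. If each subsection is applied as written, hospital costs and other costs could be expressed in dollars of different years and then added.

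**Working it through.** The Protocol gives no utility values and no in-trial QALY figure to reproduce. The weights follow exactly from its rule. The utility differences below are assumptions, shown as a range.

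**Weights, months 0-6** (u0, u1, u6 are the utilities at baseline, 1 month and 6 months; time in years)

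- Rule as written: 0.5 × (u0 + u6)/2 = 0.25·u0 + 0·u1 + 0.25·u6.
- All visits: (1/12)(u0 + u1)/2 + (5/12)(u1 + u6)/2 = (1/24)·u0 + (1/4)·u1 + (5/24)·u6, that is 0.042, 0.25 and 0.208.

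Both sets sum to 0.5 year. The rule gives the pre-treatment score half of the first six months; with all visits it has one twelfth, and the 1-month score has half.

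**Weights, months 0-24**

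| Month | 0 | 1 | 6 | 12 | 18 | 24 |
|---|---|---|---|---|---|---|
| Rule as written | 0.25 | 0 | 0.5 | 0.5 | 0.5 | 0.25 |
| All visits | 0.042 | 0.25 | 0.458 | 0.5 | 0.5 | 0.25 |

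**Omitted amount** for a between-arm difference d at 1 month (none at baseline), which the rule counts as 0

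- Fading linearly to zero at month 6: d/24 + 5d/24 = d/4.
- Fading linearly to zero at month 2: d/24 + d/24 = d/12.

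| Assumed d | Gone by month 6 (d/4) | Gone by month 2 (d/12) |
|---|---|---|
| 0.02 | 0.005 | 0.0017 |
| 0.05 | 0.0125 | 0.0042 |
| 0.08 | 0.020 | 0.0067 |

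**Mixed pattern** (assumed, PCDT minus control): d1 = −0.05 and d6 = +0.03.

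- Months 0-6, rule: 0.25 × 0.03 = +0.0075. All visits: 0.25 × (−0.05) + (5/24) × 0.03 = −0.0125 + 0.00625 = −0.00625. The sign for this interval changes.
- Months 0-24, if +0.03 persists from month 6: rule 1.75 × 0.03 = 0.0525; all visits −0.0125 + (41/24) × 0.03 = 0.03875. The sign does not change.

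**Price year.** With 24 months of follow-up (window ± 2 months) from November 2009, no subject could reach the final visit before September 2011, and the stop date is May 2016. So 2010 cannot be the last year of the trial, and the reason given for it does not fit the trial's dates. At an assumed 2% to 4% yearly inflation, 2010 and 2016 dollars differ by 1.02^6 − 1 = 13% to 1.04^6 − 1 = 27%. That is the size of the mismatch between cost components if both statements were followed.

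**The case against.** **The text is an example.** The operative sentence asks for a time-weighted average of SF-36 utilities, and the two-point means only illustrate it. An analyst following the general sentence could include the 1-month visit. That is fair, and it makes this a poorly fitting example more than a declared decision to discard data. But the example names the first six months explicitly, and nothing elsewhere brings the 1-month score in.

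**A reader might infer that early gains or harms of PCDT contribute nothing.** The Protocol does not support that. Early deaths count through survival time, early hospital costs enter the numerator, and effects still present at 6 months count through the 6-month score. Only utility differences that have faded by then are lost.

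**The d/4 value may be too large.** It assumes linear fading over five further months. Much of the SF-36 also asks about the past four weeks, so the 1-month score largely describes the first month, and a trapezoid carries it forward. Both points stand: the all-visit area is itself an approximation, and d/4 is best read as the slow-fading case.

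**The effect on the ratio may be small.** Appendix 13 uses lifetime costs and lifetime QALYs and rejects within-trial ratios, so setting the omitted amount against a two-year PTS gain would exaggerate it. A shift in QALY level that is equal in both arms cancels from the difference. Both points stand.

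**A reader might infer that 2010 dollars misstate costs.** A 2010 base applied consistently, with the index conversion that part D describes, would mainly rescale both arms. The defect is two stated bases and a justification that does not fit the trial's dates.

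**Conclusion.** The point holds in limited form. As written, the 0-6 month rule gives zero weight to a utility measured in all subjects, and between-arm differences that have faded by month 6 are not counted. The weights are exact. The size depends on assumed utility differences: 0.005 to 0.020 QALY per patient for d of 0.02 to 0.08 fading linearly to month 6, and about a third of that if the difference is gone by month 2. The direction is unknown. This is modest relative to the lifetime denominator, and the formal analysis is done only if PCDT proves efficacious and more costly. No primary, safety or clinical quality-of-life analysis is affected. The two price years are a plain inconsistency, independent of the QALY point.

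**What to change.** In Appendix 13, state that in-trial QALYs are the area under the utility curve through every SF-36 visit (baseline, 1, 6, 12, 18 and 24 months), and replace the example for the first six months with (u0 + u1)/2 for month 0-1 and (u1 + u6)/2 for months 1-6.

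Name one price year throughout Appendix 13, the last year of the trial as part B already has it, and remove the 2010 statement with its justification, so that all cost components are on the same basis.

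Both are wording changes. The 1-month SF-36v2 is already collected and scored, so no visit, form or data item is added.
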